The main effects of psilocybin are psychological. A high dose of psilocybin, which participants would receive in this study, can bring about a very broad range of profound changes in perception and consciousness during the hours of drug action. About one-third of people in our previous study reported moderate to strong feelings of fear or anxiety after receiving psilocybin. Changes in normal perception can include visual or hearing changes (pseudo-hallucinations), and unusual smells, tastes, or other bodily sensations. Participants may experience anxiety, panic, or paranoia (suspiciousness) during the period of drug action. Participants may behave in ways such as intense crying, laughing, or panic that participants might later find embarrassing. Participants may experience powerful emotions, both pleasant and unpleasant. Participants' sense of time may be altered, such that time seems to pass more quickly or slowly than usual. Participants may have a sense that the participant's body and mind have separated. The effects of psilocybin usually last about 5-7 hours.

As with other experiences of a strongly positive or negative nature, participants may have dreams and/or lasting memories of psilocybin session experiences. After the psilocybin session, there may be short-term to permanent changes in personality, attitude, or creativity.

During the period of drug action, psilocybin may also cause dizziness, nausea, vomiting, incontinence, increased pulse and blood pressure, dilated pupils, increased reflexes, tremors, and muscle twitching. A few people in an earlier study had blood pressure increases during

psilocybin sessions. Taking any drug also involves a possibility of allergic reactions such as itching, rash, or hives. Some people have reported headache starting about 7 hours after taking psilocybin and sometimes lasting into the following day. Some participants have reported leg pain lasting 1-2 days after the session.

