Psychological Distress: For cases in which acute psychological distress is insufficiently addressed with the clinician's reassurance/support, the study physician will be notified for consideration of treatment with a benzodiazepine anxiolytic (10mg oral dose of diazepam) will be given. This is based on recommendations from both historical and more recent trials with psilocybin (Grinspoon & Bakalar, 1979; Johnson et al., 2008). Participants who are experiencing acute psychological distress in addition to elevated blood pressure will first be given the 10mg of diazepam. If the participant's blood pressure remains elevated one hour following the administration of diazepam, he/she will be given 0.1mg sublingual clonidine (see below).

Acute hypertension: Blood pressure found to be elevated (i.e., systolic BP >160 or Diastolic BP >100) will be monitored at an increased frequency of every 15 minutes until resolved. If blood pressure remains greater than 160/100 for four consecutive 15-minute intervals or reaches 220/120 (without signs of end-organ dysfunction or distress), the research physician will be notified for consideration of administering anti-hypertensive medication (0.1mg sublingual clonidine). Blood pressure will be monitored every 5 minutes until resolved. Another administration of 0.1mg clonidine will be provided an hour later if the participant's blood pressure continues to be elevated above 160 systolic and 100 diastolic. If signs of end-organ dysfunction or distress and blood pressure is greater than 180 Systolic or 110 Diastolic, the research team will call 911.

Tachycardia: If the participant's heart rate is over 120 beats per minute, the study monitors will recheck vital signs every 5 minutes until resolved and instruct patient to take slow, deep abdominal breaths. If heart rate measurement goes over 150, the study monitors will notify

the on-call research physician for consideration of administering diazepam (10mg) or sublingual clonidine (0.1mg). If signs of end-organ dysfunction or distress, the study team will call 911.

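### Section 3 gives two unreconciled instructions for a participant in acute psychological distress with very high blood pressure, and does not say which prevails

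*Combined protocol and SAP*

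**What the plan says.** Both rules stand in section 3, Safety Measures, among the procedures for a medical emergency during a drug session.

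The Psychological Distress paragraph starts from distress that the clinician's support has not settled. At that point "the study physician will be notified for consideration of treatment with a benzodiazepine anxiolytic (10mg oral dose of diazepam) will be given". For distress combined with raised pressure it adds: "Participants who are experiencing acute psychological distress in addition to elevated blood pressure will first be given the 10mg of diazepam". The next step is: "If the participant's blood pressure remains elevated one hour following the administration of diazepam, he/she will be given 0.1mg sublingual clonidine (see below". The paragraph sets no upper limit on the pressure to which this sequence applies, and no exception to it.

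The Acute hypertension paragraph begins: "Blood pressure found to be elevated (i.e., systolic BP >160 or Diastolic BP >100) will be monitored at an increased frequency of every 15 minutes". Its trigger for bringing in the physician reads: "remains greater than 160/100 for four consecutive 15-minute intervals or reaches 220/120 (without signs of end-organ dysfunction or distress), the research physician will be notified"; the purpose of notification is to consider clonidine. It ends with the emergency call: "If signs of end-organ dysfunction or distress and blood pressure is greater than 180 Systolic or 110 Diastolic, the research team will call 911".

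Neither paragraph, nor any other part of the protocol, says which rule governs when both apply. The word *distress* in the 911 sentence is not defined. The Tachycardia paragraph uses the same undefined phrase as its own trigger for calling 911.

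**The concern.** A participant can meet both paragraphs at the same moment, and the next step then depends on which one the monitor follows. The combination is foreseeable. The Potential Risks section lists both anxiety or panic and raised blood pressure as effects of psilocybin, and the protocol wrote a sentence for the two together.

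The text also has to work in real time. Both monitors may be psychologists, and the study psychiatrist is onsite but may be up to 15 minutes away. The first response may therefore rest on the written rule. What is at stake is participant safety in an uncommon but serious situation. A lesser matter is the record: the same event could be logged as on-site rescue treatment or as an emergency call.

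**Working it through.** The plan has no figure to reproduce here, and no sample size, power or error rate is involved. The check applies both paragraphs to the same participant, in acute psychological distress, at a series of blood pressures.

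**Inputs, all from section 3**

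- Elevated pressure: above 160 systolic or above 100 diastolic (Acute hypertension). The Psychological Distress paragraph does not define the word, so I carry this definition over.
- Clonidine step in the distress sequence: one hour, or 60 minutes, after diazepam.
- Physician step for sustained elevation: four 15-minute intervals, 4 × 15 = 60 minutes.
- Immediate physician step: 220/120 reached (I take either component), without end-organ signs or distress.
- 911 call: above 180 systolic or 110 diastolic, with end-organ signs or distress.

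**Two readings of *distress* in the hypertension paragraph**

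- Broad: any distress, including psychological.
- Narrow: physical distress only. The participant in the table has no end-organ or physical signs.

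| Pressure (mmHg) | Distress paragraph | Hypertension paragraph, broad reading | Hypertension paragraph, narrow reading |
|---|---|---|---|
| 165/102, 175/108 | diazepam; clonidine at 60 min if still elevated | 15-min checks; physician at 60 min | 15-min checks; physician at 60 min |
| 185/105, 170/112, 200/115 | same | call 911 | 15-min checks; physician at 60 min |
| 220/120, 230/125 | same | call 911 | physician considers clonidine at once |

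**Result**

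1. In the first row the two paragraphs agree on timing, 60 minutes in each, provided diazepam is given when the elevation is found.
2. On the broad reading they part above 180 or 110: a 911 call on one side, diazepam and a one-hour clonidine decision on the other.
3. On the narrow reading they part only from 220/120, and the difference is when clonidine comes into play: at once, or after 60 minutes.
4. If end-organ signs are also present above 180 or 110, the 911 rule applies on both readings. The diazepam-first sentence makes no exception for it.

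Some divergence therefore remains whichever reading is taken.

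**The case against.** The strongest reply is that the paragraphs do different jobs. The first sets the order of drugs and the second sets escalation, so a monitor could follow both: giving diazepam does not forbid calling 911. That is fair, and a reader who infers that the instructions are opposite goes too far. But the protocol does not say that the paragraphs are to be combined, and combining them does not settle clonidine timing at 220/120.

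Three further points limit the concern.

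- A reader might infer that only the hypertension paragraph brings in the physician. The distress paragraph does so too, so notification does not separate the rules.
- A reader might infer that pressure goes unchecked for an hour after diazepam. The text does not say so. One hour is when clonidine is decided, and nothing suspends the 15-minute checks.
- The narrow reading has real support. Elsewhere in section 3 the protocol writes psychological distress in full when it means that. In the Tachycardia paragraph the broad reading would make an anxious participant with a fast heart rate a 911 case with no blood-pressure threshold, leaving little role for the on-site drugs just named.

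Against the last point, the protocol also uses the bare word for psychological states. The General Investigational Plan does so for the hourly check on well-being and for the discharge criterion, where suicidal ideation is the example. The opening of section 3 does so when it describes monitors who manage acute distress with relaxation and reassurance. The narrow reading is plausible but not settled, so a 911 divergence above 180 or 110 from psychological distress alone can be stated only conditionally.

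**Conclusion.** The point holds as an unreconciled pair of safety instructions. Its extent depends on an undefined word: the divergence starts above 180 systolic or 110 diastolic on the broad reading. On the narrow reading it starts at 220/120, apart from the missing exception when end-organ signs are present. Where the difference is clonidine timing, it is up to 60 minutes.

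The result assumes that elevated means the same in both paragraphs. The General Investigational Plan gives 140/90 as the acceptable limit on the hourly checks. If that were meant, the distress sequence would begin at lower pressures and the agreement at modest elevations would need rechecking, but the divergences at high pressure would not change.

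Two stronger inferences are not supported.

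- **Frequency.** The Potential Risks section says: "About one-third of people in our previous study reported moderate to strong feelings of fear or anxiety after receiving psilocybin". A reader might take a third of the 30 participants. That figure describes feelings of fear or anxiety in another study. It is not a rate of distress that reassurance fails to settle, nor of such distress together with pressures this high. The documents give no rate for the joint event, and screening excludes people with resting pressure above 140/90.
- **Withdrawal.** A reader might infer that the choice of paragraph decides whether a participant goes on to the second dose. The Adverse drug reaction rule makes rescue medication for psychological distress or elevated pressure a ground for withdrawal, as well as hospitalisation. It concerns the first session only, and a 911 call is not itself a hospitalisation.

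The case for acting is therefore participant safety and clarity of the text, not an expected number of events.

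**What to change.** Reconcile the Psychological Distress and Acute hypertension paragraphs so that each combination of distress and blood pressure leads to one clear course of action. Three statements would do it:

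1. What *distress* means in the hypertension and 911 sentences, with the same definition carried into the Tachycardia paragraph.
2. The blood-pressure range in which the diazepam-first, one-hour sequence applies, including what elevated means there.
3. Which rule prevails when both are met, including when end-organ signs are present.

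The medical investigators must choose the clinical content; this review proposes none. The cost is protocol wording and retraining of the session monitors. No procedure, visit or analysis is added.

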Cognitive behavioral therapy (CBT) is considered the gold-standard of empirically-based psychosocial treatments for depression (Cuijpers et al., 2013). Thus, CBT may serve as a useful, standardized foundation of psychosocial treatment to provide for patients with depression who are receiving psilocybin treatment. Additionally, psilocybin may help facilitate the uptake of CBT skills. Since psilocybin engenders greater cognitive flexibility and behavioral motivation (e.g., greater openness and social connectedness), it may help facilitate the uptake of CBT skills. Depressed individuals’ negative beliefs and unhelpful behaviors can become quite fixed, which can make treatment progress slow. Together, psilocybin may be a helpful catalyst for the cognitive and behavioral changes that are sought in CBT, and CBT may help to solidify cognitive and behavioral changes that are spurred by the psilocybin experience.

This study seeks to build on the current approaches to psilocybin treatment by combining CBT with the already-established psilocybin + PAT approach to (1) test whether CBT can be feasibly and acceptably added to the current psilocybin treatment modality and (2) to work towards protocolizing the psychosocial treatment that adjoins psilocybin drug therapy.

GENERAL INVESTIGATIONAL PLAN:

This study is a preliminary, proof-of-concept pilot to determine feasibility of the treatment methods and effect sizes. The study design is a single-group, fixed dose trial whereby 30 eligible participants will undergo 12 sessions of CBT during which two doses of psilocybin will be administered— a 10mg dose following the third session and a 25mg dose following the sixth session. Participants will be followed for an additional 3 months following treatment

termination. Study procedures will follow previously established safety guidelines (Johnson et al., 2008).

We hypothesize that psilocybin as an adjunct to 12 sessions of CBT will:

- (1) be feasible and reviewed favorably by participants, with minimal to no adverse effects;
- (2) Lead to reductions in negative thinking, increases in engagement with the environment, and improvements in depressive symptoms over the 7-month study period.

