If participants must take a nonprescription medication, participants will be asked to stop using it for 24 hours before a psilocybin session. Pain relievers containing only aspirin, ibuprofen, or acetaminophen are acceptable for normal use without special permission. Participants must also agree to leave urine samples upon request or to take a breathalyzer test to allow the study team to monitor participants' compliance with the drug and alcohol restrictions.

-Cognitive behavioral therapy (CBT)

There are no significant risks of CBT; however, CBT does involve asking patients to engage in activities that can be aversive and/or opposite of their typical thoughts and behaviors. As such, participants may experience discomfort as a result to engaging in CBT skills such as cognitive restructuring, behavioral activation, relaxation exercises.

-Depressive symptoms

Cognitive-behavioral therapy and psilocybin have been shown to have a beneficial effect of depressive symptoms. Nonetheless, it is possible that depressive symptoms will worsen during the study. An increase in depressive symptoms could be due to the study interventions (including psilocybin), not continuing in standard clinical care, or the natural course of depression. Depressive symptoms which could worsen include, but are not limited to: suicidal thoughts, low mood, feeling hopeless or guilty, fatigue, lack of pleasure, poor concentration, and change in sleep or appetite.

-Alcohol restrictions

The effects of psilocybin may interact with alcohol. This means that if participants consume alcohol while the drug is in their system, they could experience magnified or unpredictable effects of the drug, which could impair their ability to do everyday tasks such as driving an automobile. Such undesirable effects are possible for at least 24 hours following a visit to the research unit. Therefore, participants will be asked to not consume alcohol for a period of at least 24 hours before and 24 hours following the psilocybin session.

-Activity restrictions

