stress-reduction techniques, including leading relaxation exercises and providing reassurance to participants as needed. Before drug administration, hourly for the first four hours, and before discharge from the drug session blood pressure will be measured. Participant's experience of headaches and adverse visual-perceptual effects will be elicited at the end-of-drug session. Additionally, at each participant-contact (i.e., each CBT session and study assessment), a study therapist/assessor will inquire about any persisting headaches and/or visual-perceptual effects. Participants will be asked about any somatic symptoms and sensory experiences (i.e., visual, auditory, tactile, olfactory, gustatory) that have continued since the psilocybin's effects have subsided. Participants with persisting headache and/or persisting visual-perceptual effects that meet DSM-5 criteria for hallucinogen persisting perception disorder will be further assessed by a study psychiatrist to determine whether pharmacological treatment is indicated. Participants will also be asked about any alcohol use in the 24 hours following the psilocybin session.

A study psychiatrist will be onsite and available within 15 minutes for the entire duration of each drug session for an emergency and to administer rescue medication(s) as necessary.

Heart rate and blood pressure will be recorded at study's baseline screening assessment (averaged across 4 separate measurements). Heart rate and blood pressure will be re-recorded on the morning of the psilocybin drug session and monitored at hourly intervals following drug administration from 60 to 360 minutes. Heart rate and blood pressure will be taken prior to participant's discharge from the psilocybin drug session as well. Each participant's vital sign measurements and administration will be logged on the study case report form (see attached in Appendix I; pg. 25). In case of a medical emergency, the follow procedures will be followed:

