Unmanageable psychosis: Antipsychotic medication (1mg risperidone) will be available if an adverse reaction escalates to unmanageable psychosis. Antipsychotic rescue medication will be used as a last resort, as the experience of the drug is abrupt, unpleasant, intense, and may result in subsequent psychological problems (McCabe, 1977). A psychiatric emergency response team will be called for participants who continue to experience unmanageable acute psychosis at the end of the psilocybin drug session.

Allergic reaction: An antihistamine (25mg diphenhydramine) will be available in case there is any allergic reaction to the psilocybin that produces pain, itching, or swelling. If the participant begins to have trouble breathing, the study team will call 911.

In a circumstance that requires evacuation from the building (e.g., fire alarm goes off), the patient will be walked by the session monitors to UCLA's arboretum until it is safe to return to the therapy room.

Prior to discharge from each psilocybin session, participants will be given one of the study clinician's direct pager/cellphone number to call if he/she needs support or experiences any adverse events. Participants will be instructed to call 911 or go to the nearest emergency room in case of any adverse events or persisting experiences that require immediate medical attention. Within a couple of days following the drug session, participants will conduct their next weekly session of CBT. At each remaining CBT session and at each remaining study assessment (i.e., post-treatment and 3-month follow-up) study clinician will inquire about any persisting or adverse effects from the psilocybin (e.g., flashbacks or recurrent psychotic experiences). Thus, study participants will be monitored for persisting and adverse events up to 6 months following the study's first psilocybin session and 5 months following the second psilocybin drug session. In the case of any participant experiencing persisting or adverse events during the study, the symptom(s)/event(s) will be documented, presented to, and discussed with the study team, and reported to the IRB and FDA. The participant will also be scheduled to be seen by the study physician or else taken/referred to the nearest emergency room in the case of an emergency. When discharged from the study, participants will be instructed to contact their primary care doctor or mental health provider in the event of any mental health concerns.

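### No general, attribution-free adverse-event question and no adverse-event table are planned, so some harms may be under-recorded in favour of hypothesis 1

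*Combined protocol and SAP*

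**What the plan says.** The General Investigational Plan hypothesises that the combined treatment will "be feasible and reviewed favorably by participants, with minimal to no adverse effects". (The shorter hypothesis under Specific Aims leaves out the adverse-effect clause.) The design is a single group in which "30 eligible participants will undergo 12 sessions of CBT".

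The stated adverse-event questions are these:

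- **Remaining CBT sessions and assessments** (section 3, Safety Measures): the "study clinician will inquire about any persisting or adverse effects from the psilocybin (e.g., flashbacks or recurrent psychotic experiences"). The General Investigational Plan and section 1 (Potential Risks) use similar wording for the first CBT session after a drug session.
- **End of the drug session** (section 3): the participant's "experience of headaches and adverse visual-perceptual effects will be elicited at the end-of-drug session".
- **Later contacts** (section 3): persisting headache and visual-perceptual effects are asked about. In addition, "Participants will be asked about any somatic symptoms and sensory experiences", limited to those that have continued since the drug effects wore off.

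Section 1 expects a much wider set of effects. It says that "psilocybin may also cause dizziness, nausea, vomiting, incontinence, increased pulse and blood pressure" and further physical effects, and it lists anxiety, panic and paranoia. It also accepts that CBT can cause discomfort and that "An increase in depressive symptoms could be due to the study interventions (including psilocybin").

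The section on primary outcomes and statistical analysis covers feasibility percentages, the CSQ-8 mean and SD, and repeated-measures ANOVA of HAM-D and GAF. It has no adverse-event summary. The documents contain no adverse-event definition, no severity grading and no separate step for judging cause.

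**The concern.** An event is normally collected first and its cause judged later. Here the routine question builds the judgement into collection: a participant who does not link a problem to psilocybin has no stated prompt to mention it. The treatment under test is psilocybin plus CBT, and there is no control group, so attribution of single events is weak evidence and a poor filter. An event that is never recorded cannot be recovered at analysis.

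The direction is also predictable. Missed events make the adverse-effect clause of hypothesis 1 look better supported than it is, and may delay recognition of a harm. With no planned adverse-event table, nothing in the analysis would bring such a shortfall to light.

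**Working it through.** **The plan's own figure.** Section 3 gives a monitoring window of 6 months after the first dose and 5 months after the second. The visit schedule under participant worsening or non-response reproduces both: 2 + 1 + 3 = 6 months and 1 + 1 + 3 = 5 months. The contacts needed for a better question are therefore already scheduled. N = 30 is stated without power inputs, so there is nothing further to reproduce.

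**The channels side by side.**

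- *Psilocybin-effects question, every remaining visit:* broad in content, but conditional on attribution.
- *Somatic and sensory question:* broad in content, but limited to symptoms that continued. A problem that starts later falls outside it.
- *Named end-of-session elicitation:* headache and visual-perceptual effects.
- *Hourly in-session checks, two monitors present throughout:* not conditional on attribution; aimed at distress and vital signs, on the dosing day.
- *End-of-session questionnaires and semi-structured interview:* adverse-event content not stated.
- *Case report form (Appendix I):* a column for important events, on the dosing day, with no definition of important.
- *HAM-D, C-SSRS, PHQ and QIDS for suicidality; monitoring of depressive symptoms and functioning:* not conditional on attribution, but restricted to those domains.
- *Number to call:* any adverse event, but only if the participant volunteers it.

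What remains without a stated cause-free question is new-onset, transient or non-serious harm outside mood and suicidality, and CBT-related distress that is not reflected in those measures.

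**A worked case from the protocol's figures.** Section 1 puts headache onset at about 7 hours after dosing, sometimes lasting into the next day. The first session runs 6 hours, and Appendix I shows dosing at 9:00 and discharge at 3:00, which is 6 hours. The end-of-session question therefore comes about an hour before the stated onset, and the later headache question concerns persisting headache. A headache that is gone the next day can miss both. The psilocybin-effects question at the next CBT visit may still catch it, but only if the participant makes the link.

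**Scale.** The capture and attribution fractions below are assumptions; the documents give none.

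1. Section 1 says about one-third of people in a previous study had moderate to strong fear or anxiety. 30 × 1/3 = 10 expected (95% binomial range 5 to 15). Much of this should be seen by the monitors, but it is not among the effects named for end-of-session elicitation.
2. Assume a true rate of 20% and half attributed. The expected count falls from 30 × 0.20 = 6 to 30 × 0.10 = 3. P(X ≤ 1) rises from 0.80^30 + 30(0.20)(0.80^29) = 0.011 to 0.90^30 + 30(0.10)(0.90^29) = 0.184. For true rates of 10–30% with 30–50% attributed, the recorded rate runs from 0.10 × 0.30 = 3% to 0.30 × 0.50 = 15%.
3. If 0 of 30 are recorded, the one-sided 95% upper bound is 1 − 0.05^(1/30) = 9.5% with full capture. Divided by assumed capture of 80%, 50% or 25%, it becomes 11.9%, 19.0% or 38.0%.
4. An event with a 10% true rate goes unrecorded in all 30 with probability 0.90^30 = 4.2% at full capture and 0.95^30 = 21.5% at 50% capture.

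Items 2 to 4 treat every uncaptured event as lost. They do not describe in-session effects, where two observers are present and attribution is not the barrier.

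**The case against.** The strongest reply is that the protocol has many safety channels, several of them independent of cause. Panic, vomiting or tremor during dosing would happen in front of two clinicians. Release requires orientation, no acute distress needing psychiatric attention, and normal blood pressure and heart rate. Persisting or adverse events during the study are to be documented and reported with no attribution condition. The text describes what clinicians will do; it is not a question script, and in practice they may ask more openly.

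Most of this stands, and it rules out stronger readings that a reader might infer:

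- *That nothing but headache and visual effects is collected at session end.* This cannot be shown, because an interview and questionnaires of unstated content also take place.
- *That any new problem goes unasked unless blamed on the drug.* Insomnia is a counter-example: section 1 lists sleep change among depressive symptoms, and those are monitored at visits whatever the cause.
- *That harms are under-counted as a fact.* The documents support a risk, not a finding. The plan defines no adverse-event count that could be shown to be biased.

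The reply does not supply a general attribution-free question. The documentation rule acts only on events that have already surfaced, and the number to call depends on spontaneous reporting.

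**Conclusion.** The point holds as a gap in ascertainment and analysis. The routine inquiry is conditional on attribution to psilocybin, the broader somatic question is conditional on continuation, the other channels are confined to particular domains, to the dosing day or to volunteered reports, and no adverse-event summary is planned. Harms outside mood and suicidality that are new-onset, transient or non-serious, and CBT-related distress, may be under-recorded, in the direction of hypothesis 1.

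The size cannot be derived from the documents. The 20% event rate, the 50% attribution and the capture fractions are illustrations and should not be cited as estimates. The conclusion assumes that clinicians ask roughly what the text describes; an open adverse-event question in the undescribed interview or questionnaires would narrow the gap on dosing days but not at later contacts. The change should be made, but the gap does not invalidate the trial.

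**What to change.** 1. In the General Investigational Plan, section 1 and section 3, replace the attributed inquiry with an open question at every planned contact about any new or worsened health problem since the last contact.
2. At session end and at the next CBT visit, run through the effects listed in section 1.
3. Record onset, severity and duration whatever the cause, and judge relatedness to psilocybin and to CBT afterwards.
4. Add to the statistical section a table of participants and events by period (before dose 1, between doses, after dose 2, follow-up), severity and relatedness, with exact confidence intervals for the proportion of participants affected. The period before dose 1 gives some view of background events, which matters in a single-group trial.
5. Reconcile the wider collection with the section 3 sentences that send adverse events to IRB and FDA reporting and a study-physician visit. As written, every minor unrelated complaint could enter that pathway. Which events enter it is for the sponsor to decide and state.

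No new visits are needed. The cost is revised wording, a short checklist, one table and the reconciliation in item 5. The downside is more minor events recorded, some extra handling, and a less favourable adverse-event table.
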